5.9. Rescue Medication

Rescue therapy for RA is not permitted except for transient (up to 10 consecutive days) addition or increased dose of acetaminophen/paracetamol (dosed no more than 2.6 grams per day) or an opioid (not exceeding the potency equivalent of 30 mg of orally-administered morphine) If a subject is already taking stable background doses of acetaminophen/paracetamol, s/he may increase the dose up to 2.6 grams per day for up to 10 consecutive days for rescue purposes. **Subjects who require rescue for more than 10 consecutive days should be discontinued from the trial.** Acetaminophen/paracetamol may be taken for up to 5 days/week for headache, fever, or other acute, non-arthritis pain, provided the total dose (including background dose) does not exceed 2.6 grams per day.

Subjects should not be dosed with rescue treatments during the 24 hours prior to interval study visits and 7 days prior to the last day of the active dosing period (Week 8). (Note: baseline stable doses of acetaminophen/ paracetamol or opioids should NOT be discontinued in advance of study visits) (See [Appendix 11](#)).

6. STUDY PROCEDURES

Visits should occur when scheduled, within the time window indicated in the [Schedule of Activities](#). Written informed consent must be obtained prior to performing any protocol-specific procedures, including washout of prohibited medications. On study drug dosing days, PtGA and PAAP VAS measures and HAQ-DI questionnaires, should be performed prior to any other assessments. Assessments including joint counts, physician questionnaire, and pre-dose blood collections are to be performed prior to dosing unless otherwise stated.

Where possible the following order of activities should be followed during the clinic visits

1. Patient's Assessment of Arthritis Pain (VAS) and Patient Global Assessment of Arthritis (VAS)
2. ECGs
3. Vital signs
4. Physician's Global Assessment (PhGA) of Arthritis (Physician's assessment should be performed without knowledge of patient reported VAS assessments)

5. Blood and Urine Sample Collection

6. Investigational Product Dosing

6.1. Screening

For screening procedures, see [Schedule of Activities](#) and [ASSESSMENTS](#) section.

6.2. Treatment Period

For treatment period procedures, see [Schedule of Activities](#) and [ASSESSMENTS](#) section.

6.3. Follow-up/End of Study

For follow-up and end of study procedures, see [Schedule of Activities](#) and [ASSESSMENTS](#) section.

6.4. Subject Withdrawal/Early Withdrawal

Subjects may withdraw from the study at any time at their own request, or they may be withdrawn at any time at the discretion of the investigator or sponsor for safety (see also the [Withdrawal From the Study Due to Adverse Events](#) section) or behavioral reasons, or the inability of the subject to comply with the protocol-required schedule of study visits or procedures at a given study site (See [Schedule of Activities](#) for procedures to be followed at the Early Withdrawal Visit). Subjects who require rescue medication for more than 10 consecutive days should be discontinued from the trial. (See [Section 5.9](#))

Subjects who are discontinued from study treatment will enter into the Follow-up Period **with the follow-up visit occurring 1 week after the last dose whenever possible** and protocol specified follow-up procedures should be performed.

See [Appendix 4](#) for Guidelines for Monitoring and Discontinuations. The Early Withdrawal Visit applies to subjects who are randomized, received at least one dosing and then are prematurely withdrawn from the study treatment.

Subjects who withdraw from the study may be replaced at the discretion of the investigator upon consultation with the sponsor.

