This is a Phase 2a, 8 week randomized double-blind, parallel group, placebo controlled, multi-center study to assess the efficacy and safety profile of PF-06651600 in seropositive subjects with moderate to severe active rheumatoid arthritis with an inadequate response to methotrexate (up to approximately 50% of subjects may also have had an inadequate response to 1 anti-TNF α biologic DMARD).

Up to approximately 60 subjects may be randomized globally into the study to ensure at least approximately 50 subjects complete 8 weeks of active dosing (assuming a dropout rate of approximately 15%). Subjects will participate in this study for approximately 17 weeks. This includes an up to 5-week screening period, an 8 week treatment period, and a 4 week follow-up period.

After an up to 5 week screening period, eligible subjects will be randomized to receive 200 mg QD of PF-06651600 or placebo (matching tablets for PF-06651600 QD) every day for 8 weeks in a blinded fashion.

Statistical Methods:

Analysis of Primary Endpoint

The primary efficacy analysis will be conducted on Simple Disease Activity Index (SDAI) change from baseline at 8 weeks.

Analysis will include data on PF-06651600 and placebo arms.

Analysis details will be outlined in statistical analysis plan (SAP). The analysis will include: Analysis of Covariance (ANCOVA) models adjusting for SDAI baseline value; Bayesian

analysis of posterior distributions of the SDAI scores and placebo adjusted change from baseline; Advanced data visualization techniques for statistical result presentation.

The primary analysis will be conducted on intention-to-treat (ITT) population (randomized subjects with at least one post baseline value). Sensitivity analysis and handling of the missing values will be outlined in the SAP.

Analysis of Secondary Endpoints

Analyses of the secondary endpoints will be outlined in the SAP. Continuous and discrete modeling techniques will be applied whenever applicable. The statistical summaries will be presented by dose groups. The correlations between the endpoints will be analyzed.

Analysis of Other Endpoints

Analysis of other endpoints will be conducted as deemed appropriate. Continuous and discrete modelling techniques will be applied whenever applicable. Distribution summaries will be presented by means of summary tables data visualization methods.

Safety Analysis

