All clinical Adverse Events (AEs), Serious Adverse Events (SAEs), Treatment Emergent Adverse Events (TEAEs), withdrawal due to AEs, electrocardiograms (ECGs), vital signs and safety laboratory data will be reviewed and summarized on an ongoing basis during the study to evaluate the safety of subjects.

The safety analysis set will include all subjects who have received at least one dose of IP. Safety data will be presented in tabular and/or graphical format and summarized descriptively, where appropriate. All safety endpoints will be listed and summarized in accordance with Pfizer Standards. Categorical outcomes (eg, AEs) will be summarized by subject counts and percentage. Continuous outcome (eg, blood pressure (BP), pulse rate, etc) will be summarized using N, mean, median, standard deviation, etc. Change from baseline in laboratory data, ECGs and vital signs will also be summarized. Subject listings will be produced for these safety endpoints accordingly.

SCHEDULE OF ACTIVITIES

The schedule of activities table provides an overview of the protocol visits and procedures. Refer to the [STUDY PROCEDURES](#) and [ASSESSMENTS](#) sections of the protocol for detailed information on each procedure and assessment required for compliance with the protocol.

The investigator may schedule visits (unplanned visits) in addition to those listed on the schedule of activities table, in order to conduct evaluations or assessments required to protect the well-being of the subject.

Protocol Activity	Screening	Treatment Period						Follow Up/End of Study		Early Withdrawal ^b
	1	2	3	4	5	6	7	8 ^s	9	
Visit Identifier		Week 0	Week 1	Week 2	Week 4	Week 6	Week 8	Week 10	Week 12	
Study Day	Days -35 to Day 0	Day 1 ^s	Day 8	Day 15	Day 29	Day 43	Day 57	Day 71	Day 85	
Visit Window		±2 Days based on Week 0/Day 1 visit								
Informed consent	X									
Inclusion/Exclusion Criteria	X	X								
Demographics and RA history	X									
Prior RA medications check ^c	X	X								
Smoking History	X									
Medical history and Non RA medications	X									
History of Alcohol and Drug Abuse	X									
Height ^v	X									
Weight ^v	X								X	X
Contraception Check ^f	X	X	X	X	X	X	X	X ^s	X	X
Vital Signs (pulse rate, blood pressure), temperature ^d	X	X	X	X	X	X	X		X	X
Complete Physical Examination ^e	X	X							X	X
Targeted Physical Examination ^e			X	X	X	X	X			
Rash assessment	X	X	X	X	X	X	X	X ^s	X	X
ECG (12 lead) ^f	X	X					X		X	X
Chest X-ray ^g	X									
Audiogram ^y	X						X			X

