Patient Assessment of Arthritis Pain (PAAP) VAS	X	X	X	X	X	X	X	X	X	X
Patient's Global Assessment (PtGA) of Arthritis VAS	X	X	X	X	X	X	X	X	X	X
Physician's Global Assessment (PhGA) of Arthritis ^a	X	X	X	X	X	X	X	X	X	X
Health Assessment Questionnaire – Disability Index (HAQ-DI)	X	X	X	X	X	X	X	X	X	X
Serious and Non-Serious Adverse Event Assessment	X	→	→	→	→	→	→	→	X	X
Concomitant Medication & Treatments		X	→	→	→	→	→	→	X	X
Discharge from the study									X	X

Abbreviations: → = ongoing/continuous event; CRP = C-Reactive Protein; DNA = deoxyribonucleic acid ; ECG = electrocardiogram; EOS = end of study; ESR = Erythrocyte Sedimentation Rate; FACS = fluorescence-activated cell sorting; FSH = follicle stimulating hormone; HAQ-DI = Health Assessment Questionnaire – Disability Index; HBcAb = hepatitis B core antibody; HBsAg = hepatitis B surface antigen; HBsAb= hepatitis B surface antibody;

HCVAb = hepatitis C antibody; HIV = human immunodeficiency virus; hsCRP = high-sensitivity C-reactive protein; IgA, IgG, IgM, IgE = Immunoglobulin of the A, G, M, E isotypes; IGRA = Interferon Gamma Release Assay; IP = investigational product; IP-10 = IFN-gamma-inducible protein 10; IRB = institutional review board; PK = pharmacokinetic; PAAP = Patient Assessment of Arthritis Pain; PtGA = patient's global assessment; PhGA = Physician's Global Assessment; PK=Pharmacokinetics; RNA = Ribonucleic Acid; VAS = Visual Analog Scale; WONCBP = women of non-childbearing potential.

- a. Visits should occur when scheduled, within the time window indicated in the column headings. The screening visit is up to 5 weeks prior to Visit 2. On all clinic visit days, PtGA and PAAP VAS measures and HAQ-DI questionnaires, should be performed prior to any other assessments. Vital signs, ECG and blood draws should be performed as specified in [Section 7](#). Assessments including joint counts, physician questionnaire, and pre-dose blood collections are to be performed prior to dosing unless otherwise stated. Physician's assessment should be performed without knowledge of patient reported VAS assessments. Additional unscheduled assessments should be performed as clinically indicated.

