- b. See [Section 6.4](#) for guidelines on subject withdrawal/early withdrawal from the study. Any subject who prematurely withdraws from the treatment period should undergo the procedures for an early withdrawal visit and return for follow up visits if medically needed in the opinion of the PI. Document reasons for Early Withdrawal.
- c. Check and verify prior and current RA medications taken after informed consent is signed to ensure compliance with protocol eligibility criteria. Written informed consent must be obtained prior to performing any washout of prohibited medication.
- d. See [Section 7.2.5](#) for guidelines on measurement of vital signs. The same measurement method should be used consistently throughout the study.
- e. All subjects will have a dermatological full body exam at Screening Visit. Additional Physical Exams (PEs) may be performed during the study at the investigator's discretion. See [Section 7.2.2](#) for guidelines on collecting PEs.
- f. An ECG may be performed at other times, at the discretion of the investigator if there were findings during a previous examination or in the case of a new/open adverse event (AE). See [Section 7.2.6](#) for guidelines on ECGs.
- g. See [Section 7.2.8](#) for guidelines on Chest X-rays.
- h. A minimum of 8-hour fasting is required for lipid profile evaluation at Day 1, Week 4, Week 8, and EOS. Laboratory tests may be repeated once during the screening period; the last value will be used to determine eligibility. See [Section 7.2.1](#) for additional information on blood chemistry collection.
- i. Required for women of childbearing potential who do not meet the definition of non-childbearing potential as per the inclusion/exclusion criteria. Serum pregnancy test must be performed at screening. Pregnancy tests (serum/urine) may also be repeated more frequently as per request of IRBs/ECs or if required by local regulations. See [Section 7.2.4](#).
- j. See [Section 4](#) for subject eligibility criteria.
- k. HIV testing per local regulations. See [Section 4](#) for subject eligibility criteria.
- l. IGRA official reading and method, or test as per country specific guidelines, must be located in source documentation. See [Section 4](#) for subject eligibility criteria.
- m. These samples must be collected before administration of the investigational product. See [Section 7.5](#) for details.
- n. Physician's assessment should be performed without knowledge of patient reported VAS assessments.

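### For subjects who stop drug early, Section 6.4, Schedule footnote b and the discharge row conflict, and on some readings no scheduled contact reaches the 28 days of adverse-event collection in Section 8.1.4

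*Protocol*

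**What the plan says.** Three rules in the protocol apply to subjects who stop drug early.

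- Section 6.4: "Subjects who are discontinued from study treatment will enter into the Follow-up Period". On timing, it asks for a "follow-up visit occurring 1 week after the last dose whenever possible". On content, it states that "protocol specified follow-up procedures should be performed". The same section applies the Early Withdrawal visit to dosed subjects who are taken off study treatment, so it concerns the same people as the other two rules.
- Schedule of Activities, footnote b: such subjects should have the early withdrawal procedures and "return for follow up visits if medically needed in the opinion of the PI".
- Schedule of Activities, row "Discharge from the study": marked at Week 12 and also at Early Withdrawal.

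Section 8.1.4 sets the active collection period for adverse events. It applies to each subject and runs to at least 28 calendar days after the last dose. Section 4.3.1 sets the same 28-day minimum for contraception.

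The Protocol Summary and Section 3 describe "an 8 week treatment period, and a 4 week follow-up period". In the Schedule, Week 8 is Day 57, Week 10 (a telephone contact) is Day 71 and Week 12 is Day 85. The visit window is ± "2 Days based on Week 0/Day 1 visit", so it is not tied to the last dose. Under footnote o the Week 8 dose is given in the clinic.

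**The concern.** One rule makes follow-up mandatory, one makes it discretionary, and one ends participation at the Early Withdrawal visit. Sites can follow different rules and each point to written text. A site that discharges at Early Withdrawal, or stops after the one-week visit, has no scheduled occasion to ask about new events up to Day 28, although Section 8.1.4 obliges it to do so.

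Safety is a secondary objective, this is the first study of the drug in rheumatoid arthritis, and there is no data monitoring committee (Section 9.6). Early stoppers are also the group in which late events matter most: serious infection, Grade 3 rash and repeated laboratory abnormalities all lead to stopping drug (Sections 7.2.9 and 7.2.11, Appendix 5). Section 4.3.1 describes suspected teratogenicity. The Early Withdrawal visit does include a contraception check and a pregnancy test, but it is not placed at the end of the 28 days.

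Completers raise a smaller version of the same question, because their final visit is dated from Day 1 and not from their last dose.

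**Working it through.** **Inputs.** Required collection: 28 days after the last dose (Section 8.1.4). One-week visit: last dose + 7 (Section 6.4). Week 8 = Day 57, Week 12 = Day 85, window ±2 days from Day 1 (Schedule). Randomized: about 60; assumed dropout: about 15% (Section 9.1).

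**The plan's own figure.** Day 85 − Day 57 = 28 days, which is the stated 4-week follow-up. The total of 5 + 8 + 4 = 17 weeks agrees with the protocol.

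**Early stoppers, by reading.**

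1. *Footnote b and the discharge row are followed.* The Early Withdrawal visit has no date relative to the last dose, and nothing is scheduled after it unless the investigator sees medical need. The days covered cannot be derived. Zero is the worst case, not a calculated value.
2. *The one-week visit is the last contact.* 7 days covered; 28 − 7 = 21 days short.
3. *Section 6.4 governs and the scheduled contacts up to Day 85 are kept.* The earliest Week 12 visit is Day 85 − 2 = Day 83. Since 83 − 28 = 55, any last dose on or before Day 55 is covered for at least 28 days.
4. *Section 6.4 governs and the 4-week follow-up period runs from the last dose.* 4 × 7 = 28 days, so the requirement is met.

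Examples for four last-dose days:

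| Last dose | One-week visit (+7) | Day 28 reached (+28) | Days from last dose to Day 85 |
|---|---|---|---|
| Day 8 | Day 15 | Day 36 | 77 |
| Day 15 | Day 22 | Day 43 | 70 |
| Day 29 | Day 36 | Day 57 | 56 |
| Day 43 | Day 50 | Day 71 | 42 |

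**Completers (last dose at the Week 8 visit).** Nominal: 85 − 57 = 28. With only Week 12 moving: 83 − 57 = 26 to 87 − 57 = 30. With both visits moving: 83 − 59 = 24 to 87 − 55 = 32.

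**Number of early stoppers.** 0.15 × 60 = 9 expected dropouts. This is an expected count under a planning assumption. It is neither an upper bound nor the number who would gain from a fix.

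**The case against.** The strongest reply is that Section 6.4 should govern. The Schedule says of itself that "The schedule of activities table provides an overview of the protocol visits and procedures", and footnote b opens by sending the reader to Section 6.4. That section makes entry to follow-up mandatory, the follow-up period is described as 4 weeks, and nothing says that the one-week visit closes it. On that reading 28 days is reached. Section 8.1.4 binds the site whichever reading it takes, and a telephone call meets it. Other protections depend on an event: rash (Section 7.2.11), hearing decline (Section 7.2.12), late serious events (Section 8.1.4.1), pregnancy followed to completion (Section 8.4.3.1), and the instruction in Section 4.3.1 to call if contraception stops or pregnancy is suspected.

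Most of this stands. A reader might infer from the conflict that the protocol provides no mandatory, dated contact at 28 days on any reading, or that about 9 subjects will lose safety data. The documents support neither. The first fails if Section 6.4 governs. The second fails because the 9 include subjects who may withdraw consent for further data (Section 6.4.1) or be lost to follow-up (Section 6.4.2), for whom a required call would be barred or would fail.

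What the reply does not remove is the conflict itself. Section 6.4 speaks of a single follow-up visit at one week and does not say whether it replaces Day 85 or adds to it. Week 12 is the only scheduled in-clinic follow-up visit, so a site could take the one-week visit to be that visit brought forward. A site that discharges at Early Withdrawal is following a marked row of the Schedule. A duty to collect events is not the same as a scheduled contact at which to ask about them, and follow-up of known events does not find new ones.

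**Conclusion.** The conflict between Section 6.4, footnote b and the discharge row is certain. The shortfall against 28 days is conditional. It arises if a site follows footnote b and the discharge row (size not derivable) or treats the one-week visit as final (21 days). It does not arise if Section 6.4 governs and the full follow-up period applies. For completers the schedule meets 28 days exactly at nominal dates and can fall 4 days short (28 − 24) when Week 8 is held late and Week 12 early. That figure assumes that the last dose is the one given at the Week 8 visit.

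The number of subjects who would gain cannot be derived: some of about 9 expected dropouts, plus completers whose Week 12 visit comes early. No loss of safety data is demonstrated, and the primary endpoint is unaffected. Minor.

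**What to change.** 1. Amend footnote b and the discharge row to agree with Sections 6.4 and 8.1.4, and state in Section 6.4 that the one-week visit does not end follow-up.
2. Require a final safety contact at least 28 days after the actual last dose for every dosed subject who has not withdrawn consent. This includes completers whose Week 12 visit falls earlier. The content of the Week 10 telephone contact (adverse events, rash, contraception, concomitant medication) is sufficient.

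The cost is protocol wording plus a few telephone calls: about one per early stopper who can still be contacted, and one per completer with an early Week 12 visit.

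Two small edits could be made at the same time, with little or no practical consequence. Appendix 5 withdraws pregnant subjects from the study while Section 7.2.4 keeps them in it, although Section 8.4.3.1 follows the pregnancy either way. Section 6.4 also cites Appendix 4 for discontinuation guidelines that are in Appendix 5.

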6.4.1. Withdrawal of Consent

If the subject withdraws from the study, and also withdraws consent for disclosure of future information, no further evaluations should be performed, and no additional data should be collected. The sponsor may retain and continue to use any data collected before such withdrawal of consent.

Subjects should notify the investigator in writing of the decision to withdraw consent from future follow-up, whenever possible. The withdrawal of consent should be explained in detail in the medical records by the investigator, as to whether the withdrawal is only from further receipt of investigational product or also from study procedures and/or post-treatment study follow-up, and entered on the appropriate CRF page. In the event that vital status

(whether the subject is alive or dead) is being assessed, publicly available information should be used to determine vital status only as appropriately directed in accordance with local law.

6.4.2. Lost to Follow-up

Lost to follow-up is defined by the inability to reach the subject after a minimum of 2 phone calls (documented in the source documents), faxes, or e-mails as well as lack of response by the subject to 1 registered mail letter.

If a subject does not return for a scheduled visit, every effort should be made to contact the subject. All attempts to contact the subject and information received during contact attempts must be documented in the subject's medical record. In any circumstance, every effort should be made to document subject outcome, if possible. The investigator should inquire about the reason for withdrawal, request that the subject return all unused investigational product(s), request that the subject return for a final visit, if applicable, and follow up with the subject regarding any unresolved adverse events (AEs).

If it is determined that the subject has died, the site will use locally permissible methods to obtain the date and cause of death. If, after all attempts, the subject remains lost to follow-up, then the last-known-alive date as determined by the investigator should be reported and documented in the subject's medical records.

7. ASSESSMENTS

Every effort should be made to ensure that the protocol-required tests and procedures are completed as described. However, it is anticipated that from time to time there may be circumstances outside of the control of the investigator that may make it unfeasible to perform the test. In these cases the investigator will take all steps necessary to ensure the safety and well-being of the subject. When a protocol-required test cannot be performed, the investigator will document the reason for this and any corrective and preventive actions that he or she has taken to ensure that normal processes are adhered to as soon as possible. The study team will be informed of these incidents in a timely manner.

For samples being collected and shipped, detailed collection, processing, storage, and shipment instructions and contact information will be provided to the investigator site prior to initiation of the study.

